6 STUDY INTERVENTION

6.1 STUDY INTERVENTION(S) ADMINISTRATION

6.1.1 STUDY INTERVENTION DESCRIPTION

HiDO (Health Information Data Outcomes) core product is an encrypted highly secure, Web-based system on AWS used to collect, track, and report patient medication consumption for the purpose of improving the data integrity of clinical research, patient care, and public health. The platform is a 510K exempt Class I medical device that integrates medication dispensing, dose administration time, pill count and a front facing video camera to validate the right medications, at right time to the right patient. The camera logs every dose using facial recognition and provides real time consumption logs. The device dispenses up to 7 different types of medications simultaneously from 40-dram bins.

See Appendix A (HiDO Product Brochure) for hardware specifications.

Core (AMCS) features and functions include:¹

- *Patient-compliance (Real-time):* Dynamic clinical dashboards, mobile consent, adherence screen, push notifications, large font and buttons (single, multi, date, number, free-text, visual pain, VAS, etc.), multiple language capability, robust survey parameters
 - Flexible patient dashboards – Clinical Studies and Public Health populations are customized by individual principal investigators and public health departments: Validated compliance methodology and video observation therapy.
 - Conditional patient surveys – Surveys are dynamically built for an individual patient based on two levels of conditional parameters: Conditional survey assignments and questioning (branching logic within a survey takes the patient to new questions within the survey or to new surveys).
- *Patient embedded surveys:*
 - Easy-to-use patient surveys – Form-based patient surveys quickly capture adverse events and treatment side effects, easy-to-use user interface, and reporting.
 - Multiple episodes of care – Clinical dashboards that show multiple consumptions, viewed, and recorded for clinician analysis; this allows for more accurate assessment of a patient's longitudinal progress of care and better understand variability in aggregate data analysis.
 - Dynamic clinical protocols – On completion of a clinician survey, additional questions may be asked based on the protocols set up for that clinical area and a combination of clinician and patient survey responses; these protocols can be used to educate patients and track compliance with standard processes of care defined by the study protocols;

¹ Please note that the current study does not employ or test the mobile consent, patient survey, or patient education features.

such care processes could include evidence-based protocols, quality measures, red flag considerations, or study-based protocols.

- *Patient education*: tailored to patient responses, drug information and disease guidance, web links to patient education (e.g., Healthwise, CDC)
- *Reporting*: HiDO includes five types of reporting:
 - Clinician summary report – displays summary of individual patient-reported data, longitudinal adherence timeline, highlighted color coded (Green/Yellow/Red)
 - Patient-viewable mobile dashboards – tailored to patient adherence records, trend analysis of consumption, pills missed/taken, and links to websites
 - Standard aggregate data reports – aggregate survey responses, aggregate outcomes, individual summary scores (parameter-driven, save templates)
 - Standard operational reports – pending surveys, survey compliance, patient contact, etc. (parameter-driven, save templates)
 - Custom reporting via separate database – HL-7 outbound interface to client local database for client reporting
- *Workflow*: Auto-queuing of surveys (based on logic), push notifications to mobile, role-based worklists, contact log
- *Site setup configuration*: patient group, appointment types, queuing logic, site preferences, users, clinicians
- *Data transfer*: System interfaces (Scheduling system, patient portal, EMR, data warehouse); Data extracts (tab-delimited, SAS)
- *Security*: functionality security by role, standard or advanced data security by clinical area; HIPAA audit logs; HTTPS / 128-bit SSL; VPN; FTP over SSL; password security; server protection via multiple firewalls, intrusion detection system.
 - Patient Profile describes key components of a patient in an easy-to-use structure in four categories delineated by tab structures including: General, Insurance, Personal, and Clinical information for that patient; the goal is to minimize the information stored on this profile to be only the patient information needed to assign surveys (e.g., demographic, disease or condition, insurance type), assist the clinician in the clinician survey process, and provide a database suitable to support research and clinical studies; ideally, the information that is contained on the clinicians electronic medical record (EMR) is downloaded from that system and not re-entered

Video/Audio recording of the medication consumption is about 10 seconds in duration. The recording does not start until the patient unlocks the device with facial recognition and verifies the appropriate medication dispensing. The research team is HIPPA certified, and recordings are encrypted via AWS secured HIPPA storage.

6.1.2 DOSING AND ADMINISTRATION

The Principal Investigator will deliver the device to the participant's home and will assist each participant with initial device setup that includes filling the device with ART (the device holds and can dispense up to 7 different medications), installing the device app on the participant's smartphone, and configuring the device and app. The participant receives a smartphone alert when it is time to take a medication. The participant then pushes the button on the device and receives the correct medicine at the given time. In addition to tracking time, frequency, and other medication administration data, the

device video records the interaction to verify that the medication was consumed. If the patient does not respond, additional reminders are sent via SMS and read as: "It's time to take your morning medication" (for late doses scheduled for 12pm Pacific Time or earlier) or "It's time to take your evening medication" (for late doses scheduled after 12pm Pacific Time).

6.2 PREPARATION/HANDLING/STORAGE/ACCOUNTABILITY

6.2.1 ACQUISITION AND ACCOUNTABILITY

At the beginning of the study, the HiDO medication adherence platform will be delivered in person to the home of record of each participant. At the end of the 90-day intervention period, the device will be picked up from the participant's home by the PI.

6.2.2 FORMULATION, APPEARANCE, PACKAGING, AND LABELING

See Appendix A (HiDO Product Brochure)

6.2.3 PRODUCT STORAGE AND STABILITY

The HiDO device should be kept away from damp or wet areas and out of reach of pets and children.

6.2.4 PREPARATION

Not applicable.

6.3 MEASURES TO MINIMIZE BIAS: RANDOMIZATION AND BLINDING

Not applicable.

6.4 STUDY INTERVENTION COMPLIANCE

Study compliance will be assessed through manual audits of HiDO dosage logs, which verify interaction with participant through video recording, and completion of post-intervention interview and questionnaire.

6.5 CONCOMITANT THERAPY

Not applicable.

6.5.1 RESCUE MEDICINE

Not applicable.

7 STUDY INTERVENTION DISCONTINUATION AND PARTICIPANT DISCONTINUATION/WITHDRAWAL

7.1 DISCONTINUATION OF STUDY INTERVENTION

Discontinuation from HiDO platform use does not mean discontinuation from the study, and remaining study procedures should be completed as indicated by the study protocol. Although not expected to occur, if a clinically significant finding is identified after enrollment, the investigator or qualified designee will determine if any change in participant management is needed. Any new clinically relevant finding will be reported as an adverse event (AE).

7.2 PARTICIPANT DISCONTINUATION/WITHDRAWAL FROM THE STUDY

Participants are free to withdraw from participation in the study at any time upon request.

An investigator may discontinue or withdraw a participant from the study for the following reasons:

- Significant study intervention non-compliance
- If any clinical adverse event (AE), laboratory abnormality, or other medical condition or situation occurs such that continued participation in the study would not be in the best interest of the participant
- Disease progression which requires discontinuation of the study intervention
- If the participant meets an exclusion criterion (either newly developed or not previously recognized) that precludes further study participation
- Incarceration

The reason for participant discontinuation or withdrawal from the study will be recorded on the relevant Case Report Form (CRF). Participants who sign the informed consent form, and receive the study intervention, and subsequently withdraw, or are withdrawn or discontinued from the study, will be replaced as needed to ensure a sample size of at least 15 participants.

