3 OBJECTIVES AND ENDPOINTS

| OBJECTIVES | ENDPOINTS | JUSTIFICATION FOR ENDPOINTS |
|---|--|--|
| Primary | | |
| Determine the effect of automated medication adherence platform (HiDO) on medication compliance. | Mean adherence rate to ART in all patients across 90 days (quantified as (n. of doses provided — n. of doses taken) / n. of doses provided x 100) | Adherence data are automatically and continuously recorded by HiDO device, and directly confirmable through manual audit of video recordings. |
| Secondary | | |
| Determine usability of automated medication adherence platform (HiDO), as indicated by user ease of adoption (Time on Task, error rates), standardized user experience metric (SUS), and user endorsement (Net Promoter Score). | 
Measured at Week 2:
 
 • Time on Task for initial registration • Time on Task for “first click” testing • Time on Task for facial recognition setup • Time on Task for medication administration • Number and type of critical and non-critical errors • Error-free rate 
Measured after 90 days use of platform:
 
 • Score on System Usability Scale (SUS) • Net Promoter Score | 
Time on Task and error rates may be compared to published benchmarks for similar platforms.
 
According to usability.gov published by the U.S. Department of Health & Human Services, the SUS is regarded as a reliable tool to assess usability and has become the industry standard.²⁴ Results from the SUS have been published in over 1,300 publications.²⁴ It can be used on small sample sizes with reliable results and can effectively discriminate between usable and unusable systems.
 
The Net Promoter Score is based on the response to the question, “How likely is it that you would recommend our device to a friend or colleague?” on a 5-point Likert scale.
 |

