4.2 SCIENTIFIC RATIONALE FOR STUDY DESIGN

Our main goal is to demonstrate $\geq 95\%$ adherence to ART in all patients across 90 days. Admittedly, this is a very high bar. However, we are confident that we will achieve it, even for patients who have problematic use. Our informal user testing to date has shown remarkable adherence rates with the HiDO device, and these have improved as we have moved into the current version (Version 3).

For participants who completely withdraw from the study before 90 days, adherence percentage will only be calculated for the time that they participated. While we will likely glean important information from those who do drop out early, these dropouts will not affect our primary endpoint calculation. We may also fail to recruit a pool of participants that reflects the diversity of the national HIV patient population. We expect, however, to be close, and will be able to recruit a sample sufficient to intelligently plan for larger scale future testing in diverse populations. If successful, we will have demonstrated that our automated medication adherence platform is highly usable, preliminarily enables strict adherence to ART, and is ready for larger scale testing in Phase II.

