9.3 POPULATIONS FOR ANALYSES

- Modified Intention-to-Treat Analysis Dataset: participants who are enrolled for at least 7 days of the 90-day intervention period
- Per-Protocol Analysis Dataset: participants who complete the 90-day intervention period and post-study interview and questionnaire.

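### Section 7.2 lets the investigator withdraw participants for undefined non-compliance, assessed largely from the logs that supply the primary endpoint, so removal can raise the observed adherence mean

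*Combined protocol and SAP*

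**What the plan says.** - **Withdrawal.** Section 7.2 states: "An investigator may discontinue or withdraw a participant from the study for the following reasons". The first reason listed is "Significant study intervention non-compliance". No threshold, definition or adjudication is given. The reason for withdrawal is recorded on the CRF.
- **Compliance.** Section 6.4: "Study compliance will be assessed through manual audits of HiDO dosage logs". It also counts completion of the closing interview and questionnaire.
- **Primary endpoint.** Section 3: "Mean adherence rate to ART in all patients across 90 days", recorded by the device and confirmable by video audit. Section 4.1 describes an unblinded study in which investigators can see adherence trends on a dashboard.
- **After withdrawal.** Section 4.2: "adherence percentage will only be calculated for the time that they participated". The same paragraph says that dropouts will not affect the primary endpoint calculation.
- **Analysis sets.** Section 9.3 defines the mITT set as "participants who are enrolled for at least 7 days of the 90-day intervention period" and the per-protocol set as those who complete the 90 days and the closing interview and questionnaire. Neither is named as primary.
- **Replacement.** Section 7.2: withdrawn participants "will be replaced as needed to ensure a sample size of at least 15 participants".
- **Stopping the device.** Section 7.1: "Discontinuation from HiDO platform use does not mean discontinuation from the study".
- **Decision.** Sections 9.1 and 9.4.2 set H0 at below 94% and Ha at 95% or more, decided on descriptive statistics alone.

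**The concern.** The study asks how well people who miss doses adhere when they use the device; Section 5.1 enrols only people reporting less than 100% adherence. A participant who keeps missing doses is a result. If the same missed doses can also be read as non-compliance, an unblinded investigator can end that participant's observation because of the outcome.

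Nothing in the plan offsets this. The clock stops at withdrawal, the completer set drops the person, and the choice between sets is left open. Sections 10.1.6 and 10.1.7 mark safety oversight and clinical monitoring as not applicable, so no independent check on withdrawals is described. Because the decision is a plain comparison of a mean with 95%, a shift of a few points can settle the primary conclusion. Days after withdrawal are not observed, so no later choice of analysis set recovers them.

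**Working it through.** **The plan's own figure.** Section 9.2 sets 24 enrolled to give at least 15 completers at 60% completion. 15 / 0.60 = 25, and 24 × 0.60 = 14.4, so the figure reproduces approximately. It also means that 24 − 15 = 9 participants can leave before the floor of 15 calls for any replacement.

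**Illustration.** The documents give no distribution of adherence, so these values are assumed: 24 participants; 18 at 97% throughout; 6 at 90% on Days 1–30 and 40% on Days 31–90, withdrawn for non-compliance at Day 35; one dose daily. Adherence is taken as doses taken over doses due. (The Section 3 formula as printed gives the complement, which is a separate matter.)

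- Each of the six over 90 days: (0.90×30 + 0.40×60)/90 = 51/90 = 56.7%.
- Each of the six to Day 35: (27 + 0.40×5)/35 = 29/35 = 82.9%.

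| Calculation | Arithmetic | Mean |
|---|---|---|
| Everyone followed to Day 90 | (18×97 + 6×56.7)/24 | 86.9% |
| mITT, unweighted, cut at withdrawal | (18×97 + 6×82.9)/24 | 93.5% |
| mITT, doses pooled, cut at withdrawal | (18×87.3 + 6×29)/(18×90 + 6×35) = 1745.4/1830 | 95.4% |
| Per protocol | 18 at 97% | 97.0% |

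The pooled value holds for any equal number of doses per day. Section 3 does not say whether the mean is taken over participants or over doses. Eighteen remain, so no replacement is triggered.

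**Same example with constant adherence.** Let the six be at 56.7% throughout. The unweighted mITT mean stays at 86.9%. The pooled mITT mean is (1571.4 + 6×35×51/90)/1830 = 1690.4/1830 = 92.4%. Per protocol is still 97.0%.

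**Removing the lowest 9 of 24 from a completer set.** Participant adherence was simulated from a Beta distribution; means and SDs are assumed.

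| True mean (SD) | Mean after removal | P(mean ≥95%), all 24 | P(mean ≥95%), 15 left |
|---|---|---|---|
| 0.90 (0.10) | 0.959 | 0.002 | 0.78 |
| 0.88 (0.10) | 0.940 | about 0 | 0.26 |
| 0.85 (0.12) | 0.923 | about 0 | 0.05 |
| 0.68 (0.15) | 0.772 | 0 | 0 |

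Selection matters most when true adherence is close to the target. From 68%, the top of the baseline range in Section 9.2, removing nine does not approach 95%.

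**The case against.** Several stronger readings are tempting, and the documents do not support them.

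- **That non-compliance is the primary outcome itself.** The term is undefined, Section 6.4 includes the interview and questionnaire, and the device is unlocked so that medication can be taken by hand (Sections 2.2 and 2.3.3). The overlap is large, but it is not identity.
- **That the mean is inflated in every analysis set.** The unweighted mITT mean does not move when adherence is constant, and in the illustration it stays below 94% even with a steep decline. A decline is assumed, although Section 2.1 itself cites a review finding that adherence-intervention effects waned over time.
- **That poor adherers are simply swapped for better ones.** Replacement applies only as needed to keep 15, so removal, not replacement, produces the effect shown. At the planned 60% completion the expected 14.4 completers would fall just short of 15, so replacement could still arise.
- **That low adherers can readily be removed before Day 7.** The first scheduled log audit is Day 14, and Section 8.2 speaks of monthly audits from Week 4. The dashboard makes earlier action possible, but no such procedure is described.
- **That Sections 7.1 and 7.2 contradict each other.** One concerns stopping the device, the other leaving the study, and 7.2 is permissive. They are in tension.

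It is also fair to say that this is a descriptive single-arm pilot, that withdrawal reasons are recorded and that individual data are tabulated (Section 9.4.8), so removals would be visible. Visibility does not restore the unobserved days or say which mean is compared with 95%.

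**Conclusion.** The concern holds in a limited form. The plan allows withdrawal at the investigator's discretion on grounds that overlap heavily with the outcome, and then counts adherence only to that point. Removing low adherers raises the per-protocol mean; it raises the mITT mean if adherence declines or doses are pooled. On the assumed values the rise from 86.9% is 6.6 points (unweighted mITT), 8.5 points (pooled mITT) or 10.1 points (per protocol), and the last two pass 95%. The size depends on how many are withdrawn, when, and how their adherence changes, none of which the documents give. The documents do not show that the clause would be used in this way. This should be fixed; it does not by itself invalidate a pilot.

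**What to change.** - Reconcile Sections 7.1, 7.2 and 4.2. Define non-compliance, and state that missed or unlogged doses are outcome data and not by themselves a reason to end observation or leave the primary analysis. The medical and best-interest grounds in 7.2 are left unchanged.
- In Section 9.3, name one primary set: everyone who received a device, with all scheduled doses to Day 90 in the denominator. State whether the mean is over participants or pooled over doses.
- Add a sensitivity analysis that truncates at the end of device use. Otherwise ART taken by hand outside the device counts as missed. In the illustration, if logging stopped at Day 35 and later doses counted as missed, each of the six would score 29/90 = 32.2% and the mean would be (18×97 + 6×32.2)/24 = 80.8%, against 93.5% truncated. The two bracket the 86.9%.
- State that replacements add to the participants already enrolled and do not substitute for them. Report withdrawals by reason and day.

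The cost is an amendment of a few sentences and one extra summary. The drawback is a lower and somewhat conservative primary mean.

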7.3 LOST TO FOLLOW-UP

A participant will be considered lost to follow-up if he or she does not complete the post-intervention interview and questionnaire and is unable to be contacted by the study site staff.

The following actions must be taken if an enrolled participant does not complete the post-intervention interview and questionnaire:

- The site will attempt to contact the participant to determine the cause of the missed interview, and ascertain if the participant wishes to and/or should continue in the study.
- Before a participant is deemed lost to follow-up, the investigator or designee will make every effort to regain contact with the participant (where possible, 3 telephone calls and, if necessary, a certified letter to the participant's last known mailing address or local equivalent methods). These contact attempts will be documented in the participant's study file.

- Should the participant continue to be unreachable, he or she will be considered to have withdrawn from the study with a primary reason of lost to follow-up.

8 STUDY ASSESSMENTS AND PROCEDURES

8.1 EFFICACY ASSESSMENTS

Study data will be gathered through the following procedures:

- **Interaction with HiDO platform.** Dosage logs, video recording of participant during dosing
- **Questionnaires and interviews.** Self-reported medication adherence, usability metrics, open-ended consumer feedback.

8.2 SAFETY AND OTHER ASSESSMENTS

Automated medication logs from the HiDO device, and manual audits thereof, will be used to assess safety – for instance, in the unlikely event that the HiDO device contributes to substantially lower medication adherence as compared to baseline. Logs will be audited monthly beginning in Week 4 of the earliest participant enrollment.

8.3 ADVERSE EVENTS AND SERIOUS ADVERSE EVENTS

8.3.1 DEFINITION OF ADVERSE EVENTS (AE)

Adverse event means any untoward medical occurrence associated with the use of an intervention in humans, whether or not considered intervention-related (21 CFR 312.32 (a)).

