2.3 RISK/BENEFIT ASSESSMENT

2.3.1 KNOWN POTENTIAL RISKS

A potential risk to participants is breach of confidentiality, which exists both as an immediate and long-term risk. There is also an immediate risk that the platform hardware or software may malfunction in some way, which may affect data capture, data transmission, or medication dispensing. These errors may affect the reliability of the device in providing timely dosage reminders, accurate remote monitoring, and accurate dispensing of medication.

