8.4 UNANTICIPATED PROBLEMS

8.4.1 DEFINITION OF UNANTICIPATED PROBLEMS (UP)

The Office for Human Research Protections (OHRP) considers unanticipated problems involving risks to participants or others to include, in general, any incident, experience, or outcome that meets all of the following criteria:

- Unexpected in terms of nature, severity, or frequency given (a) the research procedures that are described in the protocol-related documents, such as the Institutional Review Board (IRB)-

approved research protocol and informed consent document; and (b) the characteristics of the participant population being studied;

- Related or possibly related to participation in the research (“possibly related” means there is a reasonable possibility that the incident, experience, or outcome may have been caused by the procedures involved in the research); and
- Suggests that the research places participants or others at a greater risk of harm (including physical, psychological, economic, or social harm) than was previously known or recognized.

This definition could include an unanticipated adverse device effect, any serious adverse effect on health or safety or any life-threatening problem or death caused by, or associated with, a device, if that effect, problem, or death was not previously identified in nature, severity, or degree of incidence in the investigational plan or application (including a supplementary plan or application), or any other unanticipated serious problem associated with a device that relates to the rights, safety, or welfare of participants (21 CFR 812.3(s)).

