10.1.10 PROTOCOL DEVIATIONS

A protocol deviation is any noncompliance with the clinical trial protocol, International Conference on Harmonisation Good Clinical Practice (ICH GCP), or Manual of Procedures (MOP) requirements. The noncompliance may be either on the part of the participant, the investigator, or the study site staff. As a result of deviations, corrective actions are to be developed by the site and implemented promptly.

These practices are consistent with ICH GCP:

- 4.5 Compliance with Protocol, sections 4.5.1, 4.5.2, and 4.5.3
- 5.1 Quality Assurance and Quality Control, section 5.1.1
- 5.20 Noncompliance, sections 5.20.1, and 5.20.2.

It is the responsibility of the investigator to use continuous vigilance to identify and report deviations within five working days of identification of the protocol deviation or scheduled protocol-required activity. All deviations must be addressed in study source documents and reported to the reviewing Institutional Review Board (IRB) per their policies. The investigator is responsible for knowing and adhering to the reviewing IRB requirements.

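### Device malfunction is a named risk, but a fault without a medical consequence has no assured route to a case report form, the sponsor, the IRB or a safety table

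*Combined protocol and SAP*

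**What the plan says.** Section 2.3.1 lists two known potential risks. The first is privacy: "A potential risk to participants is breach of confidentiality, which exists both as an immediate and long-term risk". The second is the device: "There is also an immediate risk that the platform hardware or software may malfunction in some way". The consequences are spelled out: "These errors may affect the reliability of the device in providing timely dosage reminders, accurate remote monitoring, and accurate dispensing of medication". Neither risk is given an expected severity or frequency.

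The event rules are in Section 8 and Section 10.1.10:

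- Adverse event (AE), 8.3.1: "Adverse event means any untoward medical occurrence associated with the use of an intervention in humans".
- Serious adverse event (SAE), 8.3.2 and 8.3.5: defined by medical outcome, and reported to the sponsor within 24 hours.
- Unanticipated problem (UP), 8.4.1: "any incident, experience, or outcome that meets all of the following criteria". The first criterion is "Unexpected in terms of nature, severity, or frequency given (a) the research procedures that are described in the protocol-related documents". The harm criterion extends to psychological, economic and social harm.
- Unanticipated adverse device effect (UADE), 8.4.1 and 8.3.6: a serious effect, or another serious problem touching rights, safety or welfare, that was not already anticipated.
- Deviation, 10.1.10: "A protocol deviation is any noncompliance with the clinical trial protocol", good clinical practice or the manual of procedures. The party at fault is the participant, the investigator or site staff.

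Section 8.2 says device logs and their manual audits serve to assess safety. Events of special interest (8.3.8), safety analyses (9.4.4) and safety oversight (10.1.6) are all marked as not applicable.

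**The concern.** The AE, SAE and causality text is written for medical events. The hazard this device brings is of another kind: it may release the wrong pill, fail to alert, fail to recognise the participant, or lose the recording. Section 2.3.1 acknowledges this, but Section 8 does not turn it into something that must be recorded, reported or counted.

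Two things are at stake. The first is participant safety. A near miss in dispensing antiretroviral therapy is the early signal of a harmful error, and it may go no further than a log entry. The second is interpretation. Section 2.2 says the data will be used to refine and finalise the platform, yet a report that followed Section 8 exactly could show no safety events although dispensing faults had occurred. A recording fault can also look like a missed dose in the primary adherence measure, so an explicit fault record would help in reading that result too.

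**Working it through.** The plan states no figure on this point and the argument needs none. The check takes each named risk through every route in the text.

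| Route | What it requires | Fault without a medical consequence | Confidentiality breach |
|---|---|---|---|
| AE (8.3.1) | A medical occurrence | Not clearly met; a fault noticed before swallowing, a missed alert or a lost recording is not in itself medical | Not met in itself |
| AE via 7.1 | A new finding judged clinically relevant | Possible for a wrong dose actually swallowed; discretionary | Unlikely |
| SAE, 24 hours (8.3.2, 8.3.5) | A serious medical outcome, or an important medical event | Not met | Not met |
| UP (8.4.1) | All three criteria: unexpected, related, greater risk than known | Nature is already named; open only on severity or frequency | Nature is already named; open on severity or frequency, and social or psychological harm counts |
| UADE (8.4.1, 8.3.6) | Serious and not anticipated | Unlikely, since it must also be serious | Possible under the rights and welfare limb if serious |
| Deviation (10.1.10) | Noncompliance by participant, investigator or site staff | Not met unless a person was noncompliant | Met if staff release data contrary to 10.1.3; not met for a leak through the cloud host or a software fault |
| Log audit (8.2) | None stated | May detect it; no reporting step | Not addressed |
| Usability errors (Section 3) | Critical and non-critical errors | May be counted as a measure of ease of adoption; no reporting duty | Not addressed |
| Safety summary (9.4.4) | None planned | Not tabulated | Not tabulated |

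Reading down the columns:

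1. For a fault without a medical consequence, no row gives an assured report. The rows that might apply (7.1, UP, UADE) each depend on judgment. For the UP and UADE rows that judgment is whether severity or frequency exceeds what was expected, and the protocol sections reviewed state no expected level for either. The consent form, which 8.4.1 also names as a reference for expectedness, is not in the text reviewed.
2. For a confidentiality breach, a leak caused by staff is a deviation that goes to the IRB under its policies, and a serious leak can be a UP. A leak through the cloud host or a software fault has no certain route.

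On exposure, 24 participants (Section 9.2) × 90 days = 2,160 participant-days if all complete. Counting only the 15 completers that Section 9.2 aims for gives 15 × 90 = 1,350, plus partial time from those who leave. No fault rate is given, so these figures cannot be turned into a number of faults.

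**The case against.** The strongest reply is that existing provisions reach further than the AE definition suggests. Much of it stands.

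- **Naming a risk does not close the UP and UADE routes.** A reader might infer that, because both risks are listed, neither can be unanticipated. The text does not support that. The first UP criterion can be met through nature, severity or frequency, and the UADE wording is similar. Listing a risk settles at most its nature. It follows that one cannot say no fault is reportable unless it causes a medical event. What remains is that the test has no stated reference level.
- **A leaked video is not simply unreportable.** UP harm includes social and psychological harm, and a release by staff is a deviation. The gap there is partial.
- **Faults may well be captured.** Section 8.2 has logs audited monthly from Week 4, and the schedule of activities marks audits at Days 14, 42, 70 and 97. A reader might also infer from the schedule that errors are recorded on only a few days. Section 4.1 lists automated user logs as a usability source, so those marks can be read as assessment times. But detection is not reporting, and 8.2 attaches no such step. Since 2.3.1 says malfunction may affect capture and transmission, logs alone may also miss some faults.
- **Suspension does not depend on a prior report.** A reader might infer that the unacceptable-risk ground in 10.1.2 would lack a trigger. The grounds there are not exhaustive and require no AE or UP report. The sponsor stores the research data (10.1.3) and investigators can see dosing data in real time (4.1).
- **A wrong dose actually swallowed** is arguably an AE, or a clinically relevant finding under 7.1, even without symptoms. The clearest unrouted case is the near miss.

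**Conclusion.** The concern holds in limited form. Followed exactly, the protocol provides no category, CRF capture, timeline or summary for device malfunction, which it lists as a known risk. A dispensing, alerting, identification or recording fault without a medical consequence can go unreported and untabulated. For confidentiality breaches the gap is confined mainly to leaks that no listed person caused.

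This is a cheap improvement that should be made, not a flaw that undermines the trial. The conclusion rests on the protocol text alone; a consent form or manual of procedures that defines these events would narrow it. It does not rest on any assumed fault rate. The documents supply none, and the number of unreported faults could be zero.

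**What to change.** 1. Add two categories to 8.3 and 8.4. *Device deficiency*: any failure or inaccuracy of dispensing, alerting, identification, recording or transmission. *Confidentiality breach*: any release of participant data or recordings to an unauthorised party, whatever the cause.
2. Record both on a CRF from device delivery to device return, whether or not harm occurred and whether or not the event was expected.
3. Capture them at the log audits and the post-intervention interview already scheduled. Reconcile the audit timing in 8.2 with the schedule of activities at the same time.
4. Report deficiencies that could have led to a serious event, and confidentiality breaches, to the sponsor and the IRB on the existing 8.4.2 timelines. Section 8.4.2 names the IRB and the coordinating centre or lead investigator, so the sponsor must be added as a recipient. The amendment should state which of its limits applies: 30 days is the one for UPs that are not SAEs. A 24-hour route for every breach is not needed to close this gap.
5. Replace the entry in 9.4.4 with a table of device deficiencies, as counts and per 100 scheduled dispenses by type, and a count of breaches.

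The cost is two definitions, one CRF page, one field in the audit form and one table. The downside is more reports and a less favourable published fault count. No clinical rule changes.
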